### **6.1.1 Screening (Visit 1: Days -7 through 0)**

Prior to or at the Screening Visit, the parent or caregiver must receive a detailed explanation of the trial and must sign the Informed Consent Form after having sufficient time to consider his/her child's participation in the trial. After the parent or caregiver has signed the Informed Consent Form and the subject has signed the Assent Form (if applicable), the following will be collected and/or performed:

- Inclusion/exclusion criteria
- Use of prior/concomitant medication up to 14 days prior to first dose of trial medication
- Parent/caregiver training on completion of HPWSQ-R
- HPWSQ-R followed by HPWSQ-R-C
- CY-BOCS (Symptoms Checklist & Severity Rating Scale)
- Food Domain of Reiss Profile
- Physical examination
- Nasal examination (See scale listed in 7.2.3)
- Medical history and demographic data
- Urine drug and alcohol screen
- Urine pregnancy test for females of childbearing potential
- Vital signs (pulse, respiration rate, blood pressure, and body temperature)
- Height and Weight
- ECG
- Clinical safety laboratory assessment: chemistry, hematology, hemostasis, urinalysis
- Nutritional phase assessment
- Adverse events

## 6.1.2 Treatment Period

### Baseline 1st day of Dosing On Site (Visit 2: Day 1)

The following will be collected and/or performed at Visit 2:

- Record use of concomitant medications
- Nasal examinations to be done within 1 hour prior to each dose (See scale listed in 7.2.3)
- Vital signs (pulse, respiration rate, blood pressure, and body temperature) will be monitored prior to and after IMP dosing at 30-minute intervals for 2 hours after each dose.
- ECG (to be done within 1 hour after morning dose)
- Laboratory samples for:
  - Pharmacokinetic sampling (3 blood samples according with the schedule specified in section 7.2.6 Clinical Laboratory Tests/Pharmacokinetic Assessments)
- Randomization (done within 24 hours prior to Visit 2 morning dose)
- HPWSQ-R followed by HPWSQ-R-C (prior to dose)
- CGI-S (prior to dose)
- IMP administration training
- Dispense IMP
- Blinded, randomized IMP dosed 3 times daily (before meals)
- Adverse events

### Visit 3: 2nd day of Dosing On Site (Visit 3: Day 2)

The following will be collected and/or performed at Visit 3:

- Record use of concomitant medications
- Nasal examinations to be done within 1 hour prior to each dose (See scale listed in 7.2.3)
- Vital signs (pulse, respiration rate, blood pressure, and body temperature) will be monitored prior to and after IMP dosing at 30-minute intervals for 2 hours after each dose.
- ECG (to be done within 1 hour after morning dose)
- Laboratory samples for:
  - Clinical safety laboratory assessment (chemistry, hematology, hemostasis, urinalysis) to be drawn post-morning dose (pre-meal)
  - Pharmacokinetic sampling (3 blood samples according with the schedule specified in section 7.2.6 Clinical Laboratory Tests/Pharmacokinetic Assessments)
- Dispense IMP
- IMP dosed 3 times daily
- Adverse events

### **3rd through 7th day of Dosing Off Site (Day 3 through Day 7)**

The following will be performed on Day 3 through Day 7 by the parent/caregiver:

- Receive/Dispense IMP
- IMP dosed 3 times daily (before meals)

### **1-Week Assessment: 8th day ( $\pm 1$ day) of Dosing Off Site (Phone Call, Day 8)**

The following will be collected and/or performed on Day 8:

- Record use of concomitant medications
- HPWSQ-R, followed by HPWSQ-R-C CGI-I
- CY-BOCS Severity Rating Scale
- Food Domain of Reiss Profile
- Receive/Dispense IMP (not part of phone call)
- IMP dosed 3 times daily (not part of phone call)
- Adverse events

### **9th through 14th day of Dosing Off Site (Day 9 through Day 14)**

The following will be performed on Day 9 through Day 14:

- Receive/Dispense IMP
- IMP dosed 3 times daily (before meals)

#### **6.1.3 Follow-up**

##### **End-of-Treatment Visit (Visit 4: Day 15)**

The following will be collected and/or performed at Visit 4:

- Record use of concomitant medications
- HPWSQ-R, followed by HPWSQ-R-C
- CGI-I
- CY-BOCS Severity Rating Scale
- Food Domain of Reiss Profile
- Physical examination
- Nasal examination (See scale listed in 7.2.3)
- Height and Weight
- Vital signs (pulse, respiration rate, blood pressure, and body temperature)
- ECG
- Urine drug and alcohol screen

- Urine pregnancy test for females of childbearing potential
- Clinical safety laboratory assessment: chemistry, hematology, hemostasis, urinalysis
- Return IMP
- Adverse events

### **Follow-up Phone Call (Day 19 ±3 days)**

Each subject will be contacted by telephone on Day 19 ( $\pm 3$  days) and assessed for adverse events.

## 7 TRIAL ASSESSMENTS

### 7.1 Assessments Related to Endpoints

#### 7.1.1 Clinical Global Impression Scales

The CGI scale ([Appendix I](#)) is a 7-point clinician rating of illness severity (0 = no illness, 6 = extremely ill), at the beginning of the trial and a 7-point clinician rating of improvement of patient condition, during and at the end of the trial ([13](#)). The scales will be administered by the Investigator or a delegated Sub-Investigator (trained and qualified by Investigator).

The CGI scales should be administered around the same time, by the same person, throughout the trial.

#### 7.1.2 Hyperphagia in PWS Questionnaires

The HPWSQ-R ([Appendix II](#)) consists of 11 questions that rate the food-seeking behavior of subjects with PWS ([11](#)). The scale will be administered by the parent/caregiver. HPWSQ-R-C ([Appendix III](#)) consists of the same 11 questions that rate the food-seeking behavior of subjects with PWS, administered by the Investigator or a delegated Sub-Investigator (trained and qualified by Investigator). The HPWSQ-R-scale should be administered by the same parent/caregiver throughout the trial. The HPWSQ-R-C-scale should be administered by the same clinician throughout the trial.

#### 7.1.3 Children's Yale-Brown Obsessive-Compulsive Scale (CY-BOCS)

The CY-BOCS ([Appendix IV](#)) is a clinician rated, semi-structured inventory of specific symptoms and symptom severity in pediatric obsessive-compulsive disorder (OCD) ([14](#)). It includes 2 primary components: the Symptom Checklist and Severity Scale. The 10 severity items are summed to produce an Obsessions Severity Score (5 items), Compulsions Severity Score (5 items), and Total score (sum of all 10 severity items). The scale will be administered by the Investigator or a delegated Sub-Investigator (trained and qualified by Investigator). Same person should perform this task around the same time, throughout the trial.

#### 7.1.4 Food Domain From the Reiss Profile

The food domain of the Reiss Profile ([Appendix V](#)) consists of 7 questions that pertain to food seeking behavior. The scale will be administered by the Investigator or a delegated Sub-Investigator (trained and qualified by Investigator), around the same time throughout the trial. It should be administered by the same person.

### 7.2 Safety and Other Assessments

#### 7.2.1 Medical History

A complete medical history will be obtained and documented at screening.

### **7.2.2 Physical Examination**

A complete physical examination including general appearance, head, eyes, ears, nose, and throat (HEENT), neck, cardiovascular, thorax/lungs, breasts, abdomen, genitourinary, musculoskeletal, lymph nodes, skin, neurological and mental status examination, will be performed by the Investigator or a delegated Sub-Investigator (a medically licensed, qualified trial team member) at Visits 1 and 4.

At screening, each category will be evaluated as normal, abnormal not clinically significant or abnormal clinically significant. Abnormal clinically significant findings at screening must be reported on the Medical History Log.

At end-of-trial, potential changes from screening to end-of-trial will be evaluated for each category. In case of changes, these will be evaluated as normal, abnormal not clinically significant or abnormal clinically significant. Abnormal clinically significant changes from screening to end-of trial must be recorded as AEs.

### **7.2.3 Nasal Examination**

Nasal examinations will be done at Visit 1, within 1 hour prior to each dose at Visit 2 and Visit 3, and at Visit 4 (anytime).

Grading will be conducted according to the following scale:

Grade 0 = no abnormal findings

Grade 1A = focal nasal mucosal inflammation, erythema, or hyperemia

Grade 1B = superficial nasal mucosal erosion

Grade 2 = moderate nasal mucosal erosion

Grade 3\* = nasal mucosal ulceration

Grade 4\* = nasal septum perforation

\*Note: After randomization, grading of 3 or 4 will be documented as an adverse event. If deemed appropriate, additional follow-up examinations will be performed at the discretion of the Investigator.

### **7.2.4 Height, Weight and Vital Signs**

Height and weight will be measured at Visit 1 and Visit 4.

Pulse, respiration rate, blood pressure, and body temperature will be measured at each visit (or at early termination) under resting conditions while the subject is seated. All blood pressure measurements should be made using the same arm while the subject is in supine position after resting for 3 minutes, and prior to any scheduled blood draws. At Visit 2 and Visit 3 - vital signs will be monitored prior to and after IMP dosing at 30-minute intervals for 2 hours after each dose.

### 7.2.5 12-Lead Electrocardiogram

After at least a 5-minute rest in a supine position, a 12-lead ECG will be obtained at each visit (or at early termination). Additional ECGs may be obtained if clinically indicated.

### 7.2.6 Clinical Laboratory Tests

#### Hematology, Hemostasis, Serum Chemistry, and Urinalysis

The following safety laboratory tests will be performed at the times specified in [Table 1](#). A 10-hour overnight fast is required prior to collecting the blood samples. Specific instructions for blood collection will be provided in a laboratory manual to the trial site.

Hematology: red blood cell count, white blood cell count, hematocrit, hemoglobin, platelet count, and differential count.

Hemostasis: prothrombin time, activated partial thromboplastin time, thrombin time, and fibrinogen

Serum chemistry: glucose, blood urea nitrogen, creatinine, potassium, sodium, chloride, calcium, total protein, albumin, total bilirubin, alkaline phosphatase, aspartate aminotransferase, alanine aminotransferase, and gamma glutamyl transferase.

Urinalysis: blood, pH, specific gravity, protein, glucose, urobilinogen, and microscopic if positive for blood or protein.

The investigator is to review laboratory results for abnormalities and clinical significance.

### Pharmacokinetic Assessments

Blood samples for PK testing will be obtained according with the following schedule:

At a Given Site	Visit 2 (Day 1) morning dose	Visit 3 (Day 2) midday dose
1st randomized patient and every third thereafter (1, 4, 7, 10, etc.)	Pre-dose, 15, and 60 min	5, 20, and 120 min
2nd randomized patient and every third thereafter (2, 5, 8, 11, etc.)	10, 30, and 180 min	Pre-dose, 15, and 60 min
3rd randomized patient and every third thereafter (3, 6, 9, 12, etc.)	5, 20, and 120 min	10, 30, and 180 min

All PK samples must be drawn prior to the next dose.:

- Visit 2 (Day 1) morning dose PK samples must be drawn prior to midday dose
- Visit 3 (Day 2) midday dose PK samples must be drawn prior to evening dose

Specific instructions for blood collection will be provided to the trial site.

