## LIST OF ABBREVIATIONS AND DEFINITION OF TERMS

### Abbreviation      Definition

ANCOVA	Analysis of covariance
CGI	Clinical Global Impression
CGI-I	Clinical Global Impression-Improvement after treatment
CGI-S	Clinical Global Impression Severity
CI	confidence interval
CL/F	apparent total clearance
C trough	plasma concentration observed immediately prior to first dose of the day
CRF	case report form
CRO	contract research organization
CY-BOCS	Children's Yale-Brown Obsessive Compulsive Scale
DMC	Data Monitoring Committee
ECG	electrocardiogram
FAS	Full Analysis Set
FDA	Food and Drug Administration
F/U	follow-up
GCP	Good Clinical Practice
HPWSQ-R	Hyperphagia in Prader-Willi Syndrome Questionnaire-Responsiveness – completed by the parent/caregiver
HPWSQ-R-C	Hyperphagia in Prader-Willi Syndrome Questionnaire-Responsiveness-Clinician – administered by the clinician
ICH	International Conference on Harmonisation
IEC	Independent Ethics Committee
IMP	investigational medicinal product
IRB	Institutional Review Board

---

Abbreviation	Definition
LOCF	Last observation carried forward
MedDRA	Medical Dictionary for Regulatory Activities
PK	pharmacokinetic
PWS	Prader-Willi syndrome
SAE	serious adverse event
SNRI	selective norepinephrine reuptake inhibitor
SSRI	selective serotonin reuptake inhibitor
V z F	apparent volume of distribution

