Prior to first dosing at the investigational site, parents/caregivers will be trained on the proper use of the nasal spray device and procedures for IMP home delivery. Parents/caregivers will be instructed to administer 3 intranasal spray pumps of blinded IMP per nostril 3 times daily before meals within the following intervals:

Morning dose: 06:00 a.m. – 09:00 a.m.

Midday dose: 11:00 a.m. – 1:00 p.m.

Evening dose: 4:30 p.m. – 6:00 p.m.

Initial IMP dosing at Visit 2 (Day 1) and Visit 3 (Day 2) will take place under observation of the site staff at the investigational site. Subject vital signs will be monitored prior to and after IMP dosing at 30-minute intervals for 2 hours after each dose. IMP will be shipped by central pharmacy directly to the subject's residence on regular intervals as needed for the duration of the Treatment Period. IMP will be administered by parents/caregivers 3 times per day before meals within the above specified dosing intervals. The IMP will require refrigeration during shipment to and during storage at the investigational site or subject's residence until administered.

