**Table 1 Schedule of Activities**

Period:	Screening	Treatment					End of Treatment Visit / Early termination visit	F/U phone call
		Baseline			1-Week Assessment			
Visit:	1	2	3				4	
Days:	-7 to 0	1	2	3-7	8 (+/-1)	9-14	15	19 (+/-3)
IMP Dosing:	NA	On site	On site	Off site			On site	NA
Assessments								
Written informed consent and assent	X							
Inclusion/exclusion criteria	X							
Prior/concomitant medication	X	X	X		X		X	
Physical examination	X						X	
Nasal examination a	X	X	X				X	
Medical history	X							
Demographics	X							
Urine drug and alcohol screen	X						X	
Urine pregnancy test	X						X	
Height and Weight	X						X	
Vital signs b	X	X	X				X	
Electrocardiogram c	X	X	X				X	
Blood samples for clinical chemistry, hematology, hemostasis, and urinalysis	X		X				X	
Blood samples for pharmacokinetics d		X	X					
Nutritional phase assessment	X							
Randomization e		X e						
HPWSQ-R and HPWSQ-R-C	X	X			X		X	
CGI-S		X						
CGI-I					X		X	
CY-BOCS	X				X		X	
Food Domain of Reiss Profile	X				X		X	
IMP administration training		X						
Dispense IMP		X	X	X	X	X		
Return IMP							X	
IMP dosing		X	X	X	X	X		
Adverse events	X	X	X		X		X	X

CGI-I=Clinical Global Impression-Improvement after treatment; CGI-S=Clinical Global Impression-Severity; CY-BOCS= Children's Yale-Brown Obsessive-Compulsive scale; F/U=follow-up; HPWSQ-R=Hyperphagia in Prader-Willi Syndrome Questionnaire-Responsiveness; HPWSQ-R-C=Hyperphagia in Prader-Willi Syndrome Questionnaire-Clinician ; IMP=investigational medicinal product

- a Nasal examinations to be done at Visit 1 (anytime), within 1 hour prior to each dose at Visit 2 and Visit 3, and at Visit 4 (anytime).
- b Includes pulse, respiration rate, blood pressure and body temperature. At Visit 2 and 3, vital signs will be monitored prior to and after IMP dosing at 30-minute intervals for 2 hours after each dose.
- c ECG to be done within 1 hour after morning dose at Visit 2 and 3.
- d Three blood samples to be collected at Visit 2 and Visit 3, according to the schedule specified in section 7.2.6 Clinical Laboratory Tests/Pharmacokinetic Assessments. All PK labs are to be done prior to subsequent dose.
- e Randomization will be done within 24 hours prior to the Visit 2, morning dose.

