#### **9.9 Population Pharmacokinetic Modeling**

Plasma carbetocin PK parameters will be estimated from serum carbetocin concentrations using population analysis. The following carbetocin PK parameters will be estimated:

$C_{trough}$ : Observed plasma concentration prior to dosing

$CL/F$ : Apparent total clearance

$V_z/F$ : Apparent volume of distribution

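### Does the pharmacokinetic schedule need changing because Ctrough is defined in two ways and no on-treatment sample precedes a first dose of the day?

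*Combined protocol and SAP*

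**What the plan says.** The protocol's List of Abbreviations defines Ctrough as the "plasma concentration observed immediately prior to first dose of the day". Section 9.9 (Population Pharmacokinetic Modeling) gives it as "Observed plasma concentration prior to dosing", with no mention of the first dose of the day. In 9.9 it stands beside CL/F and Vz/F under a common opening sentence: "Plasma carbetocin PK parameters will be estimated from serum carbetocin concentrations using population analysis".

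Table 1, footnote d, limits the pharmacokinetic sampling: "Three blood samples to be collected at Visit 2 and Visit 3". The table in section 7.2.6 assigns subjects in rotation within each site to three sampling groups. It places every draw around either the Day 1 morning dose or the Day 2 midday dose. The entry "Pre-dose, 15, and 60 min" occurs twice: for the first group on Day 1 and for the second group on Day 2. The third group has no pre-dose draw.

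The related secondary objective (section 2.1) is a population pharmacokinetic model from sparse data, and the related endpoint (section 2.2) is the population PK/PD relationship. SAP sections 6.5 and 7.1.4 leave the pharmacokinetic analysis to a separate document.

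**The concern.** The two definitions do not describe the same quantity. A sample taken before a midday dose satisfies section 9.9 but not the abbreviation list. Section 9.9 adds a second doubt: it calls Ctrough observed, yet introduces the list as things to be estimated by a model.

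The schedule seems to make this worse. The only draw that precedes a first dose of the day is the first group's Day 1 sample, taken before any study drug. Read literally, a report could give a drug-free value, a value a few hours after a dose, or an overnight value extrapolated from the model, all under one name. Ctrough is one of only three parameters named in 9.9, so it is fair to ask whether the sampling supports what the plan says it will report.

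**Working it through.** The plan states no figure for this point, so the check sets the definitions against the schedule.

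**Inputs.** Dosing windows from section 3.1.1: morning 06:00–09:00, midday 11:00–13:00, evening 16:30–18:00. Sampling table from 7.2.6. About 38 subjects at about three sites (3.2), randomized 1:1 (9.1).

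**Step 1: time since the previous dose.**
- Before a midday dose: shortest 11:00 − 09:00 = 2 h; longest 13:00 − 06:00 = 7 h.
- Before a morning dose: shortest 18:00 to 06:00 = 12 h; longest 16:30 to 09:00 = 16.5 h.
- Post-dose draws stop at 180 min, so 7 h is the longest interval any scheduled draw can reach. An overnight trough lies at least 12 − 7 = 5 h beyond it.

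**Step 2: the pre-dose draws against each wording.**

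| Pre-dose draw | Doses already given | Hours since last dose | On-treatment value under the abbreviation list? | On-treatment value under 9.9? |
|---|---|---|---|---|
| Group 1, Day 1 morning | 0 | none | No: drug-free | No: drug-free |
| Group 2, Day 2 midday | 3 + 1 = 4 | 2–7 | No: second dose of the day | Yes |
| Group 3 | no such draw | – | – | – |

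So no scheduled draw gives an on-treatment value under the abbreviation list, and one cell does so under 9.9.

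**Step 3: how many subjects that cell holds.** The rotation restarts at each site. With sites of 13, 13 and 12, the second group has 4 + 4 + 4 = 12 subjects. Over all three-site splits of 38 it has 12 or 13. With 19 of 38 on carbetocin, the expected number on active drug is 12 × 19/38 = 6.0 or 13 × 19/38 = 6.5. If arm is unrelated to sampling group, the hypergeometric 95% range is 3–9 or 4–9.

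**Step 4: what the population model has without a trough.** Each subject gives six samples: 38 × 6 = 228 in all, about 19 × 6 = 114 of them on carbetocin. Groups 1 and 2 each have one draw at 120 or 180 min, and group 3 has two. Group sizes of 14/12/12 give 14 + 12 + 24 = 50 such draws; 14/13/11 give 14 + 13 + 22 = 49; 13/13/12 give 13 + 13 + 24 = 50. Every subject has at least one.

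**Step 5: what depends on Ctrough.** No objective, endpoint or decision rule names it. CL/F and Vz/F come from the fitted model, which uses all samples at their recorded times.

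The documents give no half-life, so the difference between a 2–7 h value and a 12–16.5 h value cannot be sized from them.

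**The case for a change.** The strongest case for acting is that the correction is cheap. One definition in both places, a note on whether the value is observed or predicted, and exclusion of samples taken before first drug would be wording only. Both definitions say observed, so a model-predicted trough would contradict them, and an overnight prediction would extrapolate at least 5 h past the sampled interval. The separate analysis document can settle the meaning but cannot supply a sample that section 7.2.6 does not schedule. One existing draw could be moved without adding any: subjects are dosed on site on both days, and each would still give six samples.

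The textual mismatch stands, and so does the absence of an on-treatment draw before a first dose of the day. The rest carries less weight:

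- The observed-or-predicted doubt comes only from a shared opening sentence over a three-item list. The ordinary reading is that Ctrough is read from a sample while CL/F and Vz/F are estimated.
- Section 9.9 is the analysis text and the other wording is a glossary entry. Under 9.9 the schedule does supply a sample.
- A pharmacokinetic analyst would treat the Day 1 pre-dose sample as a blank, not as a trough. Naming the qualifying sample and reporting time since dose belong in the separate document, which is not available here.
- Moving the draw has a cost. The first group would lose its pre-drug blank, and the documents do not say that placebo samples will be assayed to replace it. A draw before the Day 1 midday dose would follow a single dose. A draw before the Day 2 morning dose would leave the first group with two pharmacokinetic draws at Visit 2 and four at Visit 3, where a separate safety sample already follows the morning dose.

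**Conclusion.** No change follows. There is a small wording inconsistency between the abbreviation list and section 9.9, of a kind the analysts will resolve when they write the pharmacokinetic analysis document. The schedule is a reasonable sparse design for the stated objective. It spreads draws from pre-dose to 180 min across three groups and gives every subject at least one draw at 120 min or later. It would fall short only if the sponsor wanted an observed overnight trough, and no objective or endpoint asks for one. Moving a draw to obtain it would give up a useful blank for a time point whose value depends on a half-life the documents do not state.

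The effect is limited to the label on one descriptive parameter, observable on treatment in 12 or 13 subjects, about 6 of them on carbetocin. The population model, the primary endpoint, the sample size and safety monitoring do not depend on it.

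This conclusion assumes three sites with the rotation restarting at each, an arm split unrelated to sampling group, and a separate document that names the qualifying sample. It also assumes that Ctrough is not used as the exposure measure in the PK/PD analysis. Nothing in the protocol or SAP gives it that role; if it had that role, the choice of definition would matter more.
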